1. STUDY DESIGN

This is a 12-month observational, multicenter, prospective study. A retrospective part is planned to include patients who have already started the treatment from the EMA approval in March 2023. In detail, the planned study design involves an enrollment phase of about 6 months and then a prospective observational period of about 12 months during which clinical, biochemical, endoscopic, and histological information will be recorded. The number of patients included in the prospective enrollment phase will then be added to the number of patients retrospectively included already on therapy since 01.03.2023. In accordance with this, for patients retrospectively included and therefore already on UPA therapy, clinical and biochemical data will be retrospectively retrieved.

2.PATIENT ENROLLMENT

Inclusion criteria: patients with established diagnosis of UC according to standard criteria (10) aged ≥ 18 years receiving UPA for moderately to severely active UC, either experienced or naïve to any advanced therapies (biologics and/or small molecule) currently available will be enrolled. These inclusion criteria are equally applied for the retrospective part of the study as stated before.

Exclusion criteria: patients unwilling or unable to give informed consent to the study. Patients meeting criteria (11) for acute severe ulcerative colitis (ASUC) will also be excluded.

3.OUTCOMES

a. PRIMARY OUTCOME

The effectiveness of UPA in patients with ulcerative colitis is evaluated in terms of clinical remission at week 8 (t1), 26 (t3), and 52 (t4) defined as a partial mayo score (PMS) ≤ 2 .

b. SECONDARY OUTCOMES

As secondary outcomes, our study will evaluate:

- Clinical response at week 8 (t1), 16 (t2), 26 (t3), 52 (t4) defined as a decrease in PMS of ≥ 3 points and $\geq 30\%$ from baseline, plus either a decrease in the rectal bleeding sub score of ≥ 1 point or an absolute rectal bleeding sub score of 0 or 1.

- Steroid-free clinical remission at t4 defined as remission without the need of any kind of systemic steroids
- Biochemical remission at t3 and t4 defined as C-reactive protein < 0.5 mg/dl and fecal calprotectin level < 250 ug/g
- Endoscopic remission at t4 defined as Mayo endoscopic sub score (MES) ≤ 1 (12)
- Histological remission at t4 defined as a Nancy index ≤ 1 (13)
- Treatment persistency at t4 defined as percentage of patients continuing UPA as maintenance treatment through week 52

c. SAFETY OUTCOMES

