We estimate a sample size with normal distribution. According to the available literature, about 250 patients are planned to be enrolled.

Continuous variables are expressed as mean \pm standard deviation (SD) and categorical variables are summarized as frequency and percentage. The Chi-square, or Fisher's exact test when

appropriate, and the independent samples T-test are applied for categorical and continuous variables respectively.

The effectiveness of UPA by clinical remission in the two groups (Partial mayo score (PMS) <2 vs PMS >2) is calculated by Chi-square or Fisher's exact test at week 8 (T1), week 16 (T2), week 26 (T3), week 52 (T4).

Another comparison in primary and secondary outcomes is performed by T Student Test (or One Way ANOVA Test with Post Hoc Multiple Comparison LSD Method) in groups of different type of patients (by gender, by range age).

The influence of risk factors on the outcomes is analyzed by multivariate binary logistic regression with Backward Wald method analysis for the effectiveness of UPA rate and with Linear Regression multivariate analysis with Backward method for week 8 (T1), week 16 (T2), week 26 (T3), week 52 (T4). P <0.05 is considered statistically significant.

STUDY TIMELINE

Project start date: 01.12.2023 (and in any case not before approval of the study by the EC)

Completion date of patients' enrollment: 01.06.2024

Data collection completion date: 01.06.2025

Data analysis: after data collection completion 01.07.2025

SUPPORT

IGIBD represents the sponsor for this study. Although there is no direct financial support, IGIBD provides the expertise of a clinical manager and a statistician for data analysis.

ETHICAL AND DATA CONSIDERATIONS

1.ETHICAL COMMITTEE

All participating centers will need Ethical Committee's approval before starting with the patients' enrollment.

2.PATIENT PROTECTION

The study coordinator ensures that this study is conducted in accordance with the Helsinki Declaration (amendments of Tokyo, Venice, Hong Kong, Somerset West, Edinburgh, Washington, Tokyo and Seoul) or with Italian laws and regulations.

The protocol was written, and the study will be conducted in accordance with the ICH guidelines for good clinical practice.

The protocol and its annexes are subject to review and approval of the Independent Ethical Committee of competence and each participating center must obtain the approval of the Ethics Committee of its institute.

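### The effectiveness test compares groups formed by the remission score itself, so it has no independent grouping factor and cannot measure effectiveness

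*Protocol*

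**What the plan says.** Under Outcomes, the Protocol's Primary Outcome is effectiveness "evaluated in terms of clinical remission at week 8 (t1), 26 (t3), and 52 (t4"), with remission "defined as a partial mayo score (PMS) ≤ 2". The Study Design section states "This is a 12-month observational, multicenter, prospective study", with a retrospective part added. The inclusion criteria admit patients "receiving UPA for moderately to severely active UC", so all are treated. No comparator, reference rate or hypothesis appears anywhere in the document.

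The Statistical Plan then says how effectiveness is assessed. The subject of its sentence is "The effectiveness of UPA by clinical remission in the two groups". It defines those groups by the score, "clinical remission in the two groups (Partial mayo score (PMS) <2 vs PMS >2"), and states that this "is calculated by Chi-square or Fisher's exact test at week 8 (T1), week 16 (T2), week 26 (T3), week 52 (T4"). It closes with "P <0.05 is considered statistically significant".

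The same section also plans frequencies and percentages for categorical variables, comparisons of outcomes by gender and age range, and regressions on risk factors.

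**The concern.** A chi-square or Fisher test on a two-by-two table needs two variables: an outcome, and a factor that sorts patients independently of that outcome. Here the outcome is remission, and the only factor named is the score that decides remission. The sentence supplies one variable and asks for a test that needs two.

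The protocol attaches this test to the effectiveness of the drug and sets a 5% significance threshold. Carried out as written, it would give an extremely small p-value that could be read as evidence that upadacitinib works, yet the same p-value would arise if almost nobody remitted.

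The sentence also departs from the Primary Outcome in two ways: its cut-offs leave out PMS = 2, and it tests at week 16.

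**Working it through.** **Inputs.** Planned enrolment of about 250 (Statistical Plan). Groups PMS <2 and PMS >2 (Statistical Plan). Remission = PMS ≤2 (Primary Outcome). Illustrative rates come from the Background: week 8, 26–33% on upadacitinib and 4–5% on placebo; week 52, 42% and 52% on the two maintenance doses. These rates serve only as assumptions. The figure of 250 is given without a rate, power or precision, so it cannot be reproduced; it is used here only as the number of patients.

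**Step 1. The literal table.** Let *a* be the number with PMS <2, *d* the number with PMS >2, and *n* = *a* + *d*. Every patient in the first group is in remission and none in the second is, so the off-diagonal cells are zero.

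Pearson chi-square (no continuity correction) = *n*(*ad* − 0·0)² / (*a*·*d*·*a*·*d*) = *n*.

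The remission rate cancels. If all 250 were classified:

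| Assumed rate | a / d | Chi-square | p | Fisher p |
|---|---|---|---|---|
| 5% | 12 / 238 | 250 | 2.6e-56 | 1e-20 |
| 26% | 65 / 185 | 250 | 2.6e-56 | 1e-61 |
| 33% | 82 / 168 | 250 | 2.6e-56 | 4e-68 |
| 42% | 105 / 145 | 250 | 2.6e-56 | 3e-73 |
| 52% | 130 / 120 | 250 | 2.6e-56 | 1e-74 |
| 90% | 225 / 25 | 250 | 2.6e-56 | 6e-35 |

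Fisher's p does move, but only with how evenly the patients split. It is larger at 90% remission than at 52%, so it does not track benefit either.

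**Step 2. Patients with PMS = 2.** If *k* patients score exactly 2, then *n* = 250 − *k* and chi-square = 250 − *k*. The table stays diagonal. These *k* patients are remitters under the Primary Outcome. With *m* remitters among 250, a rate taken over the two stated groups would be (*m* − *k*)/(250 − *k*). For *k* > 0 and *m* < 250 this is below *m*/250. The protocol gives no figure for *k*.

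**Step 3. Time points.** The Primary Outcome lists weeks 8, 26 and 52; the test sentence lists weeks 8, 16, 26 and 52. Week 16 is a time point for clinical response, a secondary outcome, but not for remission.

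**Step 4. Other readings.**
- Remitters against non-remitters on patient characteristics: a valid association analysis, but it asks who remits, not how many.
- A one-sample chi-square of remitters against non-remitters, which implies a 50/50 null: at 26%, (65−125)²/125 + (185−125)²/125 = 57.6, p = 3e-14; at 52%, (130−125)²/125 + (120−125)²/125 = 0.4, p = 0.53. The lower rate gives the smaller p-value, and no 50% benchmark is stated.

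**Step 5. What the study can deliver.** Wilson 95% intervals at 250 patients:

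| Remitters | Rate | Interval | Half-width (points) |
|---|---|---|---|
| 65 | 26% | 21.0 to 31.8 | 5.4 |
| 82 | 33% | 27.3 to 38.8 | 5.8 |
| 105 | 42% | 36.0 to 48.2 | 6.1 |
| 130 | 52% | 45.8 to 58.1 | 6.1 |

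**The case against.** The strongest defence is that the protocol never says remission will be cross-tabulated against itself. The preceding sentence assigns chi-square or Fisher tests to categorical variables and the t-test to continuous ones, which is the usual wording for comparing the characteristics of two groups. On that view the two PMS groups are remitters and non-remitters, compared at each visit as a lead-in to the risk-factor regression, and the label of effectiveness is merely loose.

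Part of this stands. The diagonal table, and with it the extreme p-value, follows only from the literal reading. But the sentence names no characteristic to compare. Gender, age range and risk factors have their own sentences, and the charitable reading still does not evaluate effectiveness.

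A reader might also infer more than the text supports:
- *That this is the only effectiveness analysis.* It is not. The section also plans a logistic regression for effectiveness and comparisons of the outcomes by gender and age range.
- *That the remission rate will not be reported.* Categorical variables are to be given as frequencies and percentages, so a remission percentage is planned.
- *That the missing confidence interval is itself a protocol error.* Interval methods are commonly left to a statistical analysis plan, and one may exist. The point here is that the test the protocol does fix is unsuitable.
- *That a significant result is certain.* This holds only on the literal reading, with both groups non-empty and enough patients classified.

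**Conclusion.** The concern holds in this form: the test assigned to the effectiveness of upadacitinib has no independent grouping factor. Read literally it is circular, with chi-square equal to the number classified (250 and p about 2.6e-56 if all planned patients were classified, fewer if some score exactly 2). Read charitably it is an association analysis. Neither reading measures effectiveness, and the descriptive percentage and the regression elsewhere in the section do not change that.

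This is a stated rule that is wrong, not detail left for a later document, because the protocol itself fixes the test, the groups and the threshold. The same sentence contradicts the Primary Outcome on PMS = 2 and on week 16.

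The conclusion about circularity needs no assumed remission rate. It rests on all patients receiving upadacitinib and on no comparator being named; the protocol does not itself call the design single-arm. The interval widths assume 250 evaluable patients and the Background rates.

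**What to change.** Replace the test sentence in the Statistical Plan with wording such as:

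> Effectiveness is estimated as the proportion of patients in clinical remission (PMS ≤2) at weeks 8, 26 and 52, each with a two-sided 95% confidence interval (Wilson method).

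Wilson is one suitable choice among several. Use PMS ≤2 throughout, in line with the Primary Outcome. If remission at week 16 is wanted, list it under the outcomes as a non-primary time point.

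Keep chi-square or Fisher tests only for comparing remission between independently defined patient groups, such as by gender or age range.

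The denominator and the handling of missing PMS values are separate matters that this change does not settle. The cost is protocol wording: no added patients, visits or data, and a simpler analysis.

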BACKGROUND AND RATIONALE	4
AIM OF THE STUDY	5
METHODS	6
• STUDY DESIGN	6
• PATIENT ENROLLMENT	6
• OUTCOMES	6
1. primary	
2. secondary	
3. safety	
• PROCEDURES	8
STATISTICAL PLAN	9
STUDY TIMELINE	9
SUPPORT	10
ETHICAL AND DATA CONSIDERATIONS	10
REFERENCES	13

BACKGROUND AND RATIONALE

Ulcerative colitis (UC) is a chronic inflammatory bowel disease (IBD) affecting the colon and rectum. Despite the availability of multiple therapeutic options for patients with UC, achieving short-

term and long-term disease control remains challenging, and symptoms negatively impact on patients' quality of life (QOL) (1,2). Indeed, approximately two-thirds of patients fail to obtain or maintain remission after 1 year even with the use of current biologics agents. Janus kinase (JAK) pathways regulate immune signaling and are implicated in IBD pathogenesis (3). Upadacitinib (UPA) is an oral, selective, small molecule JAK inhibitor engineered to have preferential inhibitory effects for JAK1 that has recently received approval in Italy for the treatment of UC. UPA selectivity might allow the evaluation of higher doses, potentially providing greater efficacy without increasing some of the reported safety issues associated with JAK2 and JAK3 inhibition. The efficacy of UPA is supported by phase 2 (4) and phase 3 (5) explanatory trial.

In a phase 2 (4) dose-ranging, placebo-controlled induction study, patients with moderately to severely active ulcerative colitis received UPA at the following doses: 7,5 mg, 15 mg, 30 mg, and 45 mg once daily. UPA 45 mg once daily showed an optimal benefit–risk profile with the highest efficacy rates and no clinically relevant increase in safety events compared with lower doses and was therefore selected for the phase 3 induction dose. Considering a potentially more favorable long-term safety profile, two doses (15 mg and 30 mg once daily) lower than the induction dose were selected as the phase 3 maintenance doses; both doses also showed superior efficacy versus placebo in the phase 2b study.

In the induction analysis of a phase 3 trial (5), the primary endpoint, clinical remission at week 8, was achieved by 26-33% of patients receiving UPA versus 4-5% of patients receiving placebo (both $p < 0,0001$).

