Moreover, in the maintenance analysis of the same trial, the primary endpoint defined as clinical remission at week 52, was achieved by 42% of patients receiving UPA 15 mg once daily, and 52% patients receiving UPA 30 mg once daily, and 12% of patients receiving placebo ($p < 0,0001$).

At present, the efficacy and safety data of UPA come mostly from clinical trials. Few real-world experiences (6,7) are available in the literature and one report is a multicenter case series from our center that is planned to be presented during the upcoming XIV IGIBD national congress. As stated in drug data sheet (8), UPA is indicated in the treatment of adult patients with moderate to severe active ulcerative colitis (evaluated with Mayo Score – disease activity index (9)) who have had an inadequate response, have lost the response or are intolerant to conventional therapy or a

biological agent. UPA is available in three doses 45,30 and 15 mg. Patients receive 45 mg orally every day for 8 or 16 weeks (depending on clinical judgment and according to risk-benefit evaluation) as induction therapy. At the end of induction period, patients in clinical remission will receive UPA 15mg or 30mg (depending on clinical judgment and according to risk-benefit evaluation) every day as maintenance therapy.

According to reported adverse events in both registrative trials (4,5), serious adverse events and adverse events leading to discontinuation of treatment were less frequent in the UPA 45 mg group than in the placebo group (serious adverse events 3% vs 5-6%; adverse events leading to discontinuation 2% vs 5-9%).

The most frequently reported adverse events in the maintenance part of the trial were nasopharyngitis (12-15%), creatine phosphokinase elevation (5-6%), arthralgia (6-10%) and upper respiratory tract infection (4-6%). Events of cancer, adjudicated major adverse cardiac events, or venous thromboembolism were reported infrequently. There were no treatment-related deaths.

Despite the drug presents an adequate safety profile, careful analysis of indications and contraindications must therefore be carried out by medical personnel before starting the drug.

AIM OF THE STUDY

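### Remission is defined as PMS ≤2 but analysed as PMS <2 versus PMS >2, so a patient scoring exactly 2 is a remitter with no analysis group

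*Protocol*

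**What the plan says.** Two places in the protocol state the cut-off for clinical remission.

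- **Methods, 3. Outcomes, a. Primary outcome.** Remission is "defined as a partial mayo score (PMS) ≤ 2". The visits are given as "clinical remission at week 8 (t1), 26 (t3), and 52 (t4").
- **Statistical Plan.** Effectiveness is analysed through "clinical remission in the two groups (Partial mayo score (PMS) <2 vs PMS >2"). This "is calculated by Chi-square or Fisher's exact test at week 8 (T1), week 16 (T2), week 26 (T3), week 52 (T4").

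The two statements differ in the cut-off (≤2 against <2) and in the visits (week 16 is added). The Statistical Plan also gives the planned size, "about 250 patients are planned to be enrolled", and the threshold "P <0.05 is considered statistically significant".

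**The concern.** The cut-off decides who counts as a success on the primary outcome. Under the Outcomes section a patient with PMS 2 is a success. Under the Statistical Plan that patient is in neither group. An analyst following the Statistical Plan must drop the patient, count the patient as a failure, or depart from the text. A later analysis plan could follow either sentence and still claim to follow the protocol.

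The effect is not confined to one test. Steroid-free remission at week 52 is built on the same notion of remission, and the planned logistic regression for effectiveness needs a yes/no remission variable. Both inherit the ambiguity.

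There is also a timing problem. The Study Design section admits patients treated since 01.03.2023, and the Study Timeline starts the project on 01.12.2023. That is 275 days, or 275/7 ≈ 39 weeks. The earliest patients would be past weeks 8, 16 and 26 before the study begins, so some outcomes may already be known while the cut-off is still open. Nothing suggests that anyone intends to choose the cut-off on the data, but the text as it stands would allow it.

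**Working it through.** **Step 1. Put each score against both statements.** PMS is taken as an integer from 0 to 9. The protocol does not state the range, but the gap at 2 does not depend on it.

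| PMS | Outcomes section (≤2) | Statistical Plan group |
|---|---|---|
| 0, 1 | remission | <2 |
| 2 | remission | neither |
| 3 to 9 | not in remission | >2 |

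Exactly one integer score is left out, and it is a remission score.

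**Step 2. The plan's own figure.** The only design figure is the sample size of about 250. It cannot be reproduced, because no expected rate, effect, power or precision is given for it. The contradiction does not depend on it. It is used below only for scale.

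**Step 3. Formulas.** Let N = 250 (every patient scored at the visit), r = the remission rate under PMS ≤2, and q = the share of all patients with PMS exactly 2.

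- Patients without a group: N × q
- Reported rate if they are dropped: (r − q)/(1 − q)
- Reported rate if only PMS <2 counts, over all N: r − q

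**Step 4. Inputs.** The protocol gives no value for q, so 5%, 10% and 15% are assumed. For r, 45% is a hypothetical value. For context, the Background quotes remission rates from the phase 3 trial: at week 8 it "was achieved by 26-33% of patients receiving UPA versus 4-5% of patients receiving placebo", and at week 52 it "was achieved by 42% of patients receiving UPA 15 mg once daily, and 52% patients receiving UPA 30 mg once daily". The protocol does not say that the trial endpoint was PMS ≤2, so 33% and 52% serve only to bracket a plausible range.

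**Step 5. Results.** Patients without a group: 250 × 0.05 = 12.5; 250 × 0.10 = 25; 250 × 0.15 = 37.5.

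| r | q | Dropped | Counted as failures |
|---|---|---|---|
| 33% | 5% | 0.28/0.95 = 29.5% | 28% |
| 33% | 10% | 0.23/0.90 = 25.6% | 23% |
| 33% | 15% | 0.18/0.85 = 21.2% | 18% |
| 45% | 5% | 0.40/0.95 = 42.1% | 40% |
| 45% | 10% | 0.35/0.90 = 38.9% | 35% |
| 45% | 15% | 0.30/0.85 = 35.3% | 30% |
| 52% | 5% | 0.47/0.95 = 49.5% | 47% |
| 52% | 10% | 0.42/0.90 = 46.7% | 42% |
| 52% | 15% | 0.37/0.85 = 43.5% | 37% |

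**Step 6. Scale.** The half-width of a 95% interval at r = 45% and N = 250 is 1.96 × √(0.45 × 0.55/250) = 6.2 percentage points. With q = 10% the shift is 45 − 38.9 = 6.1 points (dropped) or 10 points (counted as failures). The choice of cut-off can therefore move the estimate by as much as its sampling error, or more.

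**Step 7. Check the remedy.** With groups ≤2 and >2, scores 0, 1 and 2 fall in the first group and 3 upward in the second. Every score has one group, and the first group is the remission group of the Outcomes section.

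**Step 8. Visits.** The Outcomes section lists remission at weeks 8, 26 and 52. Week 16 appears there only for clinical response. The Statistical Plan's test of remission at week 16 therefore has no matching outcome.

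**The case against.** The strongest reply is that this is a typing slip. The upper group, >2, is the exact complement of ≤2, and only the Outcomes section sets out a definition; the Statistical Plan has a shorthand in brackets. The intent is probably ≤2. This is likely right, but it is a reason to correct the sentence. The Statistical Plan is the instruction the analyst follows, and it gives a different cut-off for the primary outcome. A symbol lost in converting the PDF is not a good explanation, since ≤ and ≥ come through correctly in the Outcomes section.

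A second reply is that the sentence describes a test, not the estimate. Categorical variables are summarised separately as counts and percentages, and a rate taken from the Outcomes definition would be unaffected. This stands in part: the bias arises only if the bracketed groups are used to classify patients. The protocol does not say which statement prevails, so the risk is real but not certain.

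Third, the percentages are illustrations. That stands. Only the direction is established by the text. Both the 5–15% share and the 45% rate are assumptions, and so is complete scoring of 250 patients at each visit.

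Fourth, the week 16 test is a minor matter. That also stands. Week 16 is a planned evaluation point, the sentence does not call it primary, and an extra visit does not bias the others.

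Finally, the sentence appears to compare remission between groups that are themselves defined by remission, and it names no second factor for the Chi-square table. Correcting the symbol does not cure that. It is a separate weakness and does not remove the contradiction.

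**Conclusion.** The concern holds. The protocol states the primary outcome's cut-off twice, in two ways that cannot both be followed, and no other section reconciles them. Applying the Statistical Plan as written can only lower the reported remission rate, never raise it. Under the assumptions above, the loss from a true 45% runs from about 3 points (5% at PMS 2, dropped) to 15 points (15% at PMS 2, counted as failures). The contradiction itself needs none of these assumptions; it needs only that a patient can score exactly 2. The week 16 mismatch is also real but secondary in importance.

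**What to change.** In the Statistical Plan, replace the bracketed groups by **PMS ≤2 versus PMS >2** (equivalently 0–2 versus 3 or more). State that this is the remission definition of the Outcomes section and applies wherever remission is used, including steroid-free remission and the logistic regression.

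Limit the primary analysis to weeks 8, 26 and 52. Label remission at week 16 as secondary and add it to the list of secondary outcomes. While the sentence is open, name the factor across which remission is to be compared.

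The cut-off correction is one sentence, and the week 16 label adds one line in the Outcomes section. Data collection does not change, because the score itself is what is assessed. The correction should be dated and made before the outcome data are analysed.

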Another aspect that will be assessed is the safety profile of the drug during all the period in terms of

- Any adverse events
- Serious adverse events are defined as any adverse reaction that results in death, is life-threatening, requires hospitalization or prolongation of existing hospitalization, results in persistent disability according to European Medicines Agency definition. There will be a focus on opportunistic Infections (principally Herpes Zoster infections), thrombo-embolic events and major adverse cardiovascular events (MACE)

Since the reporting of adverse events is the responsibility of the prescribing physician of the drug, it will be necessary for the investigating physician of each participating center to provide the report to AIFA.

4.PROCEDURES

To evaluate these outcomes, as previously described, the study involves 5 main evaluation points that are normally part of our clinical practice (see also Flow-Chart file):

T0 (baseline visit): at the beginning of the induction period of UPA treatment, general information regarding the disease will be collected.

T1 (8 weeks): clinical status will be re-evaluated with a telephone consultation and/or clinical examination if an objective examination is needed. At this time, as reported in the drug data sheet, the need for continued induction therapy and drug dosing will be assessed.

T2 (16 weeks): clinical status will be re-evaluated with a telephone consultation and/or clinical examination if an objective examination is needed. At this time, as reported in the drug data sheet, drug dosing will be assessed.

T3 (26 weeks): the clinical status will be re-evaluated with a telephone consultation and/or clinical examination if an objective examination is needed. At this time, as reported in the drug data sheet, drug dosing will be assessed. In addition to the previous evaluation, a C-reactive protein blood sample and fecal collection will be requested for a calprotectin assay.

T4 (52 weeks): the clinical status will be re-evaluated with a telephone consultation and/or clinical examination if an objective examination is needed. At this time, as reported in the drug data sheet, drug dosing will be assessed. A C-reactive protein blood sample and fecal collection will be requested for a calprotectin assay. If possible, a colonoscopy with biopsy sampling will be requested.

STATISTICAL PLAN

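### Clinical remission is the primary outcome at three visits but is analysed at four, no visit leads, and one unadjusted P<0.05 rule covers the subgroup and risk-factor tests

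*Protocol*

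**What the plan says.** Under METHODS, 3. OUTCOMES, the Protocol evaluates effectiveness by "clinical remission at week 8 (t1), 26 (t3), and 52 (t4) defined as a partial mayo score (PMS) ≤ 2". It gives no order among these visits and no rule for combining them. Week 16 enters the outcome list only as a secondary visit for another endpoint: "Clinical response at week 8 (t1), 16 (t2), 26 (t3), 52 (t4"). Under PROCEDURES it is also a scheduled contact: "T2 (16 weeks): clinical status will be re-evaluated with a telephone consultation".

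The STATISTICAL PLAN evaluates effectiveness by "clinical remission in the two groups (Partial mayo score (PMS) <2 vs PMS >2"), using Chi-square or Fisher's "exact test at week 8 (T1), week 16 (T2), week 26 (T3), week 52 (T4"). It then adds two further sets of tests:

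- Comparisons of primary and secondary outcomes by gender and age range, using a t-test or one-way ANOVA with LSD post hoc comparisons. No visits are named.
- Backward-selected regressions on risk factors: a logistic model for the effectiveness rate, and a linear model followed by the list of weeks 8, 16, 26 and 52.

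One rule closes the section: "P <0.05 is considered statistically significant". On design, the Protocol states: "This is a 12-month observational, multicenter, prospective study". It describes no control group.

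**The concern.** Two current sections of one document disagree on the visits at which the primary endpoint is assessed. A statistical analysis plan that is not shown cannot explain that away, because the conflict lies within the Protocol.

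With no lead visit, no single result is fixed in advance as the answer to the study question. Week 8 falls at the first induction assessment and week 52 in maintenance; the Protocol's own background reports the phase 3 results at those two times as separate primary endpoints. They need not tell the same story, and a report free to choose between them can lead with the more favourable one.

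The second stake is the factor tests. Nothing marks them as exploratory, LSD does not itself adjust pairwise p-values for the number of comparisons, and backward selection picks factors on the same data. A factor below 0.05 at one visit out of four could be presented as a predictor of effectiveness.

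**Working it through.** **1. Visits side by side**

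| Week | Remission in OUTCOMES | Response in OUTCOMES | Remission in STATISTICAL PLAN |
|---|---|---|---|
| 8 | primary | secondary | analysed |
| 16 | not listed | secondary | analysed |
| 26 | primary | secondary | analysed |
| 52 | primary (steroid-free remission is secondary) | secondary | analysed |

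The only mismatch is remission at week 16.

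**2. Is a lead visit implied elsewhere?** The sample size could have revealed one. It is given as about 250 patients, with no remission rate, precision, effect size, power or visit attached. It cannot be reproduced and points to no visit. The secondary outcomes lean towards week 52, since every one of them includes it, but the text does not make that visit primary.

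**3. Chance of a spurious factor finding (illustration)**

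Inputs:
- Threshold 0.05, from the STATISTICAL PLAN; two-sided is assumed, as sidedness is not stated.
- Four visits, as listed for the linear regression.
- One factor with no effect at any visit.
- Correlation between the visit-specific test statistics, which is not in the documents and is assumed over a range.

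If the tests are independent, the chance of at least one P<0.05 is 1 − (1 − 0.05)^4 = 1 − 0.8145 = 0.185.

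For equally correlated two-sided z-tests (simulation, 1,000,000 draws):

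| Assumed correlation | At least one P<0.05 in four visits |
|---|---|
| 0 | 18.5% |
| 0.3 | 17.3% |
| 0.5 | 15.6% |
| 0.7 | 13.1% |
| 0.9 | 9.4% |

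The range of about 13% to 18.5% covers correlations from 0.7 down to 0. These figures model neither backward selection nor the LSD comparisons.

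**4. Does this carry over to the effectiveness analysis?** No. The two groups in the remission test are defined by the Partial Mayo Score at the visit, which is remission status itself. The test compares remitters with non-remitters on the quantity that separates them, so it tests no hypothesis about upadacitinib, and no error rate for a drug effect builds up over visits.

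**5. What an estimate would offer.** With 250 evaluable patients and an assumed remission rate of 0.50, the 95% half-width at one visit is 1.96 × √(0.50 × 0.50 / 250) = 0.062, or 6.2 percentage points.

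**The case against.** The strongest reply is that this is an uncontrolled observational study that will estimate remission at several times. All three primary visits are listed in advance, no success rule is stated, and reporting three rates needs no split of alpha. An extra remission analysis at week 16, where clinical status is assessed anyway, is then a small listing gap. Multiplicity methods and interval reporting are also commonly left to the statistical analysis plan.

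Much of this stands, and it rules out several stronger readings:

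- A reader might infer that week 16 is not an outcome visit at all. It is one, for clinical response; only remission at week 16 is unlisted.
- A reader might infer that the chance of wrongly declaring the drug effective is inflated across visits. The remission test has no such hypothesis, so the documents do not support this.
- A reader might infer that gender and age tests are run at all four visits. That sentence names no visits. In the regression sentence the visit list clearly attaches only to the linear model; whether it also covers the logistic model is unclear.
- A reader might multiply up to many factors: ten factors at four visits would give 1 − 0.95^40 = 87%. The Protocol gives no number of factors, and tests on the same patients at successive visits are not independent.
- Formal adjustment such as Holm's is debatable in a study of this kind, and its absence is not an error.

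The reply does not remove the disagreement between two sections on the primary endpoint's visits, nor the missing lead visit, which belongs in the protocol. Nor does it cover the factor tests: these do test hypotheses, and the Protocol itself sets a significance threshold for them.

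**Conclusion.** The point holds in a limited form. The three-against-four mismatch and the absence of a lead visit rest on the text alone and need no assumption. That the three primary visits have equal standing is an inference from silence, as is treating the four-visit analysis as the primary one; the STATISTICAL PLAN does not use that label, although the endpoint is the primary one.

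The multiplicity element concerns factor screening only. Its size, roughly 13% to 18.5% per null factor over four visits instead of 5% at one, is illustrative and depends on the assumed correlation; at 0.9 it falls to 9.4%. The consequence is selective emphasis on a visit or a factor, not a false efficacy claim. It should be corrected, and the correction changes what the study can conclude more than how it is run.

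**What to change.** - Make OUTCOMES and STATISTICAL PLAN agree: either list remission at week 16 as a secondary outcome or remove it from the remission analysis.
- Name one visit as primary before data analysis and make the other visits secondary. Week 52 would fit the 12-month design and is shared by every secondary outcome.
- State that the effectiveness result is the remission rate at each visit with its 95% confidence interval, in place of a test between remitters and non-remitters.
- Label subgroup and risk-factor p-values exploratory, and say which visits each model covers.
- In the same amendment, reconcile the remission cut-off. OUTCOMES includes a score of exactly 2 in remission, while the STATISTICAL PLAN's two groups leave it out of both. This is a separate point in the same sentence.

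Cost: two visits lose primary status, factor findings must be stated more cautiously, and the amendment may need ethics committee review, possibly at each centre, since every centre needs its own approval. No visit or procedure is added.
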